#### Plasma Biomarkers: IGF Pathway:

Studies have shown that dysregulation of the IGF pathway and an increase in insulin-like growth factor 1 (IGF-1) can result in increased risk of breast cancer. A previous study has shown that 2 months use tamoxifen can reduce IGF-1/IGFBP-3 and another study showed the same with raloxifene. We have previously shown an increase in IGFBP-1 with 6 months use of anastrozole. Currently, there is no data related to the modulation of the IGF pathway, therefore we aim to study modulation of this pathway induced by 4-OHT treatment.

#### ***Rationale for including Alcohol and Tobacco Assessment Questionnaires***

Increasing evidence suggests that tobacco and alcohol use are risk factors in the development of intraepithelial neoplasia and cancer. In addition, tobacco and alcohol use may adversely affect agent intervention, for example by altering the safety profile or metabolism of a drug. Standardized assessments of tobacco and alcohol use during clinical trials will aid in understanding the potential relationship between the use of these products and clinical endpoints or cancer prevention biomarkers. Therefore, NCI, DCP is including assessment of tobacco and alcohol use at baseline and Month 12 to determine the potential impact

of tobacco and alcohol use on 1) treatment toxicity and symptom burden, and 2) the efficacy of treatment intervention.

In summary, the overall objective is to evaluate whether daily application of 4 mg of 4-OHT topical gel (2 mg per breast) versus placebo lowers breast density in women with mammographically dense breast.

### 3. SUMMARY OF STUDY PLAN

We will conduct a prospective, randomized, double-blind, placebo-controlled phase II study of 4-hydroxytamoxifen topical gel in women with mammographically dense breast.

Women age 40-69 years, or less than 40 years if Gail risk is greater than 1.66% will be eligible. All participants will have mammographically dense breast (heterogeneously dense or extremely dense based on ACR BIRADS 4th or 5th edition classification).

Women with prior annual mammograms showing heterogeneously dense or extremely dense breasts will be approached for enrollment into the study prior to their next annual mammogram. Informed consent must be obtained prior to starting any further study procedures. Consenting should be done prior to next annual mammogram (the baseline study mammogram). Once the participant has signed consent, the mammography center should be alerted not to delete the raw images. In centers where raw images are stored, consent can occur after the annual mammogram that will serve as the baseline mammogram for the study. The mammogram must be within 3 months of randomization. Raw images must be obtained from the Baseline, 12-Months and 24-Months mammograms. Mammography reports from the previous annual mammography visit should also be obtained. If it is not possible to see a participant in person for the Month 12 visit during the COVID-19 pandemic, the visit will be rescheduled per the COVID-19 Contingency Plan (see Section 7 for details) and mammograms will be rescheduled accordingly and corresponding raw images from that mammogram will be obtained.

158 women with confirmed eligibility will be randomized 1:1 to 2 arms. Participants in Arm A will receive 4-OHT, participants in Arm B will receive placebo. The daily dose of gel application is 4 mg (2 mg per breast). The 4-OHT gel or placebo will be applied topically in 1 pump actuation to each breast. Women will undergo baseline toxicity assessment, blood draw and instructions on how to apply the gel and an optional breast core biopsy. While women will not be stratified by menstrual cycle (as there is minimal, if any, effect of the menstrual cycle on our primary endpoint of mammographic density), their menstrual cycle will be recorded. Randomization will be performed stratified by study site and baseline breast density category (heterogeneously dense (C) or extremely dense (D)). The research nurse/coordinator will call the participants at Day 7-14 to verify the start of study agent, and at months 3 and 9 for toxicity assessment. The participants will return to the clinic at 6 months for toxicity assessments, physical exam and vital signs, lab tests and plasma biomarker blood draws, collection of unused study agent, and to receive additional study agent. At 12 months, the participants will return to clinic for toxicity assessment, collection of unused study agent, collection of blood for plasma biomarkers, standard of care mammogram, and the optional breast core biopsy, if she opted to participate in this part of the study. At 24 months the research staff will collect the standard of care bilateral mammogram images; the participants will not be approached. For the period of the COVID-19 pandemic, if participants cannot be seen in person at Months 6 and/or 12, the COVID-19 contingency plan will be followed (see Section 7 for details).

#### 4. PARTICIPANT SELECTION

##### 4.1 Inclusion Criteria

- 4.1.1 Women age 40-69 years, or less than 40 years if 5-year breast cancer Gail risk is  $\geq 1.66\%$ .
- 4.1.2 Mammographically dense breast (heterogeneously dense (C) or extremely dense (D), based on ACR BIRADS© fifth edition classification or heterogeneously dense (3) or extremely dense (4), based on ACR BIRADS© fourth edition classification) in either breast.
- 4.1.3 ECOG performance status  $\leq 1$  (Karnofsky  $\geq 70\%$ ; see Appendix A)
- 4.1.4 Participants must have normal organ and marrow function defined as ALL of the below:
  - White Blood Cells  $\geq 3,000/\text{microliter}$
  - Platelets  $\geq 100,000/\text{microliter}$
  - Total bilirubin  $\leq 1.5 \times \text{institutional upper limit of normal (ULN)}$
  - AST (SGOT)/ALT (SGPT)  $\leq 1.5 \times \text{institutional upper limit of normal (ULN)}$
- 4.1.5 Participant must have a gynecology examination within the last 5 years (gynecology examination is not required if participant had a hysterectomy).
- 4.1.6 Premenopausal women using a hormonal or non-hormonal Intra-Uterine Device (IUD) birth control method will be eligible, if they have been on the same IUD for at least 3 months prior to enrollment and plan to continue using the same method throughout the study.
- 4.1.7 Women who are using postmenopausal hormones, and are planning to continue the same regimen through the study intervention are eligible to participate.
- 4.1.8 Willingness to avoid exposing breast skin to natural or artificial sunlight (i.e. tanning beds) for the duration of the study.
- 4.1.9 Ability to understand and the willingness to sign a written informed consent document.

##### 4.2 Exclusion Criteria

- 4.2.1 History of allergic reactions attributed to compounds of similar chemical or biologic composition to 4-OHT gel.
- 4.2.2 Uncontrolled intercurrent illness including, but not limited to, ongoing or active infection, symptomatic congestive heart failure, unstable angina pectoris, cardiac arrhythmia, thromboembolic disease, or psychiatric illness/social situations that would limit compliance with study requirements.
- 4.2.3 Pregnant, unwilling to use adequate contraception during study treatment duration, had given birth, or nursed at any time during the last 12 months (see footnote 1 below).

- 4.2.4 Women with a previous history of invasive breast cancer or bilateral DCIS or current untreated DCIS. Women with a history of cancer within the last 3 years, except for non-melanoma skin cancer. Women with unilateral DCIS (with or without radiation therapy) are eligible as long as they have an unaffected breast.
- 4.2.5 Prior bilateral breast surgery (mastectomy, segmental mastectomy, or breast augmentation surgery including breast implants or breast reductions).
- 4.2.6 Women with “mosaic mammographic screening views”, i.e., whose larger breast size precludes being imaged within a single mammographic screening view.
- 4.2.7 Women with active liver disease.
- 4.2.8 Women with a uterus and abnormal uterine bleeding, or prior diagnosis of endometrial hyperplasia, endometrial polyps, or endometrial cancer.
- 4.2.9 Prior use of SERMS and AIs, except for a maximum of 3 months and at least 12 months prior.
- 4.2.10 Skin lesions on the breast that disrupt the stratum corneum (e.g., eczema, ulceration).
- 4.2.11 Treatment with any investigational drug or investigational biologic within 30 days of initiating study treatment or during the study.

 The effects of 4-OHT gel on the developing human fetus at the recommended dose are unknown. For this reason and because tamoxifen is known to be teratogenic, all heterosexually active women who may become pregnant must agree to use a reliable non-hormonal contraceptive method or a hormonal IUD during the study and for 2 months after completing study medications. Reliable nonhormonal methods of contraception include barrier contraception and an Intra-Uterine Device (IUD). Hormonal IUDs are also allowable methods of birth control. [Note: Women who had tubal ligation or had a partner who had undergone a vasectomy (and are monogamous) are eligible for the study and are not required to use barrier contraception.

### **4.3 Inclusion of Women and Minorities**

Men and women less than 40, unless they have sufficient breast cancer risk that they would be undergoing mammography screening, are excluded because these populations are not routinely screened using mammography. Women of all races and ethnic groups are eligible for this trial.

### **4.4 Recruitment and Retention Plan**

Participants will be recruited for enrollment on this trial from mammographic screening units and breast clinics at participating institutions, with particular attention to enhancing racial, ethnic and socioeconomic diversity. Prior to enrollment, the study will be discussed in detail with the participant, and possible toxicities will be presented. The informed consent document will be reviewed with the participant by the study physician or other medical staff authorized by the participating institution to obtain Informed Consent. To facilitate accrual, information about the trial will be advertised, for example, on the websites of participating institutions.

Refer to the study-specific Recruitment and Retention Plan for more details.

## 5. AGENT ADMINISTRATION

Intervention will be administered on an outpatient basis. Reported AEs and potential risks are described in Section 6.2.

### 5.1 Dose Regimen and Dose Groups/Gel Application

Participants will self-administer the 4-OHT/ placebo gel. The participants will be instructed to apply the gel daily to both breasts, freshly washed, either by washcloth, shower, or bath, preferably in the morning (in order to minimize potential transfer to the partner at night). If morning shower is not possible, the participant will wash the breasts with a washcloth before gel application, to remove the prior day's dose. If a morning swim is planned, application should be after the swim. No washing or immersion in water should occur for at least 4 hours following gel application. The gel should not be used near fire, flame or while smoking since it is flammable due to alcohol. Once dry, the gel is no longer flammable. Detailed instructions regarding application are in Appendix B and a demonstration of gel application will occur during the Randomization visit. A model bust may be used to demonstrate to the patient how to apply the gel if such a model is available. The treated breasts should be covered at all times to avoid transfer to other people and protect from natural or artificial sunlight; contact is permitted after the treated area has been washed with soap and water and washing is allowable after a minimum of 4 hours post-application.

Each 4-OHT/placebo gel canister will contain ~100 mL gel product and will be metered to dispense 2 mg of 4-OHT/placebo gel per pump. There will be 200 mg of 4-OHT in 100 mL of 4-OHT gel. Because there are 80 reliable doses per canister, each canister will provide 40 days of therapy at 2 mg/day/per breast. Daily dose of 4-OHT/placebo gel application is 4 mg (2 mg per breast). Five gel canisters will be given to the participant at the time of randomization and should be returned at Month 6 visit. One (1) ml (one actuation of the pump) should be applied each day per breast. At Month 6 visit five additional canisters will be provided to the participant and the containers provided at the time of randomization will be collected. All containers will be collected at the Month 12 visit.

#### **COVID-19 Contingency Plan:**

During the COVID-19 pandemic, if a participant is not able come for an in person visit at Month 6, instruct the participant during the phone visit to keep all used canisters and to bring the canisters to the next in person clinic visit. Five additional canisters will be provided to the participant (via mail or picked up in person). At Month 12, participants will be telephone consented to extend the gel application and instructed to keep using the gel until their mammogram can be rescheduled up to 18 Months. In addition they will be provided five additional canisters (via mail or picked up in person) and all canisters will be collected at the mammogram visit.

### 5.2 Run-in Procedures

N/A

### 5.3 Contraindications

Participants are to avoid exposure of the treated breast skin to natural or artificial sunlight. This includes sunbathing or the use of tanning beds with the breasts exposed. Also, women who have dermatologic conditions causing the breakdown of skin in the area of gel application should not use 4-OHT gel.

#### 5.4 Concomitant Medications

All medications (prescription and over-the-counter), vitamin and mineral supplements, and/or herbs taken by the participant will be documented on the concomitant medication CRF and will include: 1) start and stop date, if known; if unknown, mark “unknown” in the database, 2) dose and route of administration, and 3) indication.

#### 5.5 Dose Modification

For grade 1-2 toxicities, no dose modifications will be made. If a grade 2 toxicity possibly, probably, or definitely related to study drug re-occurs, the gel application will be stopped until the adverse event resolves, then full dose will be reintroduced. If the toxicity re-occurs for a 3rd time, the participant will be taken off study drug. For grade 3 toxicity possibly, probably, or definitely related to study drug, gel application will be stopped until the adverse event resolves, then full dose will be reintroduced. If the adverse event re-occurs, the participant will be taken off study drug. Participants experiencing Grade 4 toxicities of any attribution will be taken off study drug.

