## 8.4 Off-Agent Criteria

Participants may stop applying the study gel for the following reasons: completed the protocol-prescribed intervention, adverse event or serious adverse event, inadequate agent supply, noncompliance, concomitant medications, medical contraindication, or pregnancy. Participants will continue to be followed, if possible, for safety reasons and in order to collect endpoint data according to the schedule of events. We plan to accrue 7 more participants per arm to account for women who are not evaluable because they discontinued participation prior to meeting criteria for contributing evaluable results. Women who discontinue the agent for any reason should continue on study if possible to allow for collection of their routine mammograms.

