14. Do not wash your breasts or immerse in water (bath, swim) for at least 4 hours following application of the gel. If this is not possible, delay application of the gel that day until after immersion, and be sure to follow all the above instructions. If you regularly swim in the morning, it is better to apply the gel afterwards, after your shower.
15. After use, replace the cap on the bottle.
16. Avoid exposure of the treated breast skin to natural or artificial sunlight. This includes sunbathing or the use of tanning beds with the breasts exposed. Also, if you have dermatologic conditions causing the breakdown of skin in the area of gel application, you should not use 4-OHT gel.

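### Section 5.5 should say that gel is held for skin breakdown of any grade, and should exempt related thromboembolic events from its full-dose restart (minor safety and consistency correction)

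*Combined protocol and SAP*

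**What the plan says.** Section 5.5 (Dose Modification) opens with "For grade 1-2 toxicities, no dose modifications will be made". It then gives three further rules:

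- Recurrent related grade 2: "If a grade 2 toxicity possibly, probably, or definitely related to study drug re-occurs, the gel application will be stopped". Full dose resumes once the event resolves, and a third occurrence ends treatment.
- Related grade 3: "For grade 3 toxicity possibly, probably, or definitely related to study drug, gel application will be stopped until the adverse event resolves". Full dose is then reintroduced, and a recurrence ends treatment.
- Grade 4: "Participants experiencing Grade 4 toxicities of any attribution will be taken off study drug".

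Section 5.3 (Contraindications) says that "women who have dermatologic conditions causing the breakdown of skin in the area of gel application should not use 4-OHT gel". Appendix B item 16 gives the participant the same instruction: "if you have dermatologic conditions causing the breakdown of skin in the area of gel application, you should not use 4-OHT gel". Neither sets a limit by grade or attribution. Exclusion criterion 4.2.10 points the same way at entry.

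Section 8.4 lists adverse event and medical contraindication among the grounds for coming off gel, under the words "Participants may stop applying the study gel for the following reasons". It also asks that women who stop the agent stay on study, where possible, so that their mammograms can be collected.

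**The concern.** Appendix B is written for use at home during treatment, so the skin rule is more than an entry check. If skin breaks down on treatment at a low grade, a site following 5.5 to the letter would leave the dose unchanged while the woman's own sheet tells her not to apply the gel. Nothing cross-refers 5.3 and 5.5. Section 5.3 also does not say whether gel is paused or stopped for good, or when it may restart. The point concerns broken skin only, not itching or burning on intact skin.

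The second issue is separate and is a missing safeguard, not an inconsistency. After a related grade 3 event resolves, 5.5 directs a return to full dose for every event type. Section 2.1 names thromboembolic events among the risks of oral tamoxifen, and 4-OHT is an active metabolite of tamoxifen (Section 6.1). Most investigators would not want a protocol line pointing them to restart after such an event.

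At stake are participant safety and uniform handling across seven sites. No error in the statistical plan is claimed.

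**Working it through.** The plan gives no figure to reproduce on this point, so the check is a side-by-side reading for skin breakdown in the application area.

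| Event | 5.5 read literally | 5.3 and Appendix B item 16 | Result |
|---|---|---|---|
| First grade 1 | No change | No gel | Differ |
| Recurrent grade 1 | No change | No gel | Differ |
| First grade 2 | No change | No gel | Differ |
| Recurrent grade 2, unrelated | No change | No gel | Differ |
| Recurrent grade 2, related | Hold; off drug at third occurrence | No gel | Agree on stopping |
| Grade 3, related | Hold; off drug at recurrence | No gel | Agree on stopping |
| Grade 3, unrelated | Silent | No gel | 5.3 applies alone |
| Grade 4 | Off drug | No gel | Agree |

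The gap is the first four rows.

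**How often it might arise.** Section 6.2 gives application site reactions of 4% on active gel against 0% on placebo, over six months at 4 mg/day, described as burning and itching. With 158/2 = 79 women per arm:

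- 0.04 × 79 = 3.2 women with any site reaction;
- 0.08 × 79 = 6.3 if the rate doubled over 12 months (an assumption).

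Breakdown would be an unknown share of these, possibly none. Unrelated conditions such as eczema could add to it, in either arm. Section 6.2 also lists exfoliative dermatitis, without grade, count or site. Its phase 1 summary reports only mild pruritus.

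**How it would be seen.** In the 7.1.1 schedule, adverse events are collected at Day 7-14 and Months 3, 6, 9 and 12. Three of these five contacts (Day 7-14, Months 3 and 9) are by telephone, with no skin examination. Breast examination takes place at Months 6 and 12. The diary has missed-dose boxes and a symptom column, and is reviewed at Months 3, 6, 9 and 12.

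**Thromboembolic events.** Grade 4 is covered, since drug stops at any attribution. For a related grade 3 event, 5.5 calls for restart at full dose after resolution. Section 8.4 allows an investigator to stop for an adverse event or contraindication, but no section requires it.

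**The case against.** The strongest reply is that the two sections do different jobs. Section 5.3 says who should not use the gel at all, and 5.5 manages toxicity in women who may. A general grade rule does not displace a specific contraindication in the same chapter. Section 8.4 then supplies the route off gel, and its permissive verb only introduces a list of reasons. Pregnancy is on that list too, and Section 7.3 flatly forbids dispensing after a positive test. The woman applies the gel herself and her sheet tells her not to, and a stop would normally show up through diary review or breast examination.

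Most of this stands. It is why the point is a missing cross-reference and not a flat contradiction. It does not supply the hold, the restart condition or the statement of precedence.

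A reader might go further and infer three things that the documents do not support:

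- **That women are being harmed.** No low-grade breakdown in the application area is documented, and no data on absorption through broken skin are given. The one broken-skin result, in rabbits with scarified flanks (Section 6.2), was comparable for active and placebo gel.
- **That participants are never told to report skin problems.** Appendix B's only line about notifying the doctor concerns a faulty pump, but the consent pages are not in the file, so this cannot be concluded.
- **That the thromboembolic omission is a pressing hazard.** Section 2.2 reports that risk factors for these events did not rise with the gel. Section 4.2.2 excludes uncontrolled thromboembolic disease at entry, and Section 11.2.2.2 brings a serious event to the medical monitor by telephone within 24 hours.

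**Conclusion.** The point holds as a minor safety and consistency correction. Section 5.5 lacks a skin-breakdown exception in four situations where 5.3 and Appendix B say not to use the gel. Section 5.3 is best read as governing, but that is left to the reader, and the action to take is not defined. Section 5.5 also directs full-dose restart after a resolved related grade 3 thromboembolic event, and no other section requires otherwise.

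The likely size is small: perhaps 3 to 6 site reactions of any kind in 79 active-arm women, on the assumption that the six-month rate carries over or doubles, with an unknown and possibly zero share involving broken skin. It might be inferred that the gap weakens the trial's statistical case, but it does not. Section 13.4 analyses every randomized woman with both mammograms regardless of compliance, so sample size, stated power and the primary analysis population are unchanged.

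**What to change.** Add to Section 5.5:

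> *Notwithstanding the grade rules, if skin breaks down in the application area, gel is held until the skin has healed, at any grade and whatever the attribution (see 5.3). The existing recurrence, grade 3 and grade 4 stopping rules still apply. Gel is not reintroduced after a thromboembolic event judged at least possibly related to study drug; the participant remains on study for mammograms (see 8.4).*

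No new limit on recurrences is needed for grade 1 or unrelated breakdown. Neither 5.3 nor 5.5 asks for one, and it could end treatment in women whose skin had healed.

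The change adds no visits, tests or participants. Its downside is a few interruptions or discontinuations, in either arm, because the placebo gel shares the roughly 75% alcohol base (Section 6.1). Section 5.6.1 tolerates 25% missed days: 0.25 × 365 = 91 days over a year. A hold of 14 to 28 days (an assumption) uses 14/365 = 3.8% to 28/365 = 7.7%. Holds totalling more than about 91 days, or a permanent stop before month 9, would make a woman non-compliant under 5.6.1. She would still be in the primary analysis if her 52-week mammogram were obtained. For skin breakdown, 5.3 already directs the same women off gel, so the sentence mainly makes current intent explicit.
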